### 10.2.14 Defining Rescue Medications

Rescue medications are the medications that were

1. Recorded as rescue medication in the CRF form, started within 48+4 hours (or 3 days where the time is missing) of a study drug exposure for an HAE attack,

or,

2. Recorded as concomitant medication in the CRF form, started within 48+4 hours (or 3 days where the time is missing) after a study drug exposure, is not ongoing, and had an indication that include 'HAE' or 'Swelling'.

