Medications provided for rescue therapy will be denoted as rescue medications on the appropriate CRF. Antihistamines (diphenhydramine, loratadine, cetirizine, etc.) and glucocorticoids are considered ineffective for the alleviation of an acute HAE attack. If administered during an acute attack that occurs during the study, they should be recorded as concomitant medications but will not be considered as rescue medications.

If rescue medication is provided, the investigator will document the drug name, amount, time, route of administration, frequency, and duration administered.

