### 7.2 Analysis Populations

The following populations will be used in the analysis:

- The Efficacy Population will consist of those subjects who were treated with icatibant for their first and any additional attacks during the study.
- The Safety Population will consist of those subjects who were treated with icatibant at least once during the study (irrespective of the presence of an HAE attack).

All efficacy analyses will be performed on the Efficacy Population. The corresponding tabular summaries will be presented by the icatibant exposure number. For the initial icatibant exposure, the analyses will be presented by the pubertal status (Pre-pubertal vs. Pubertal/Post-pubertal) and overall; for the subsequent icatibant exposures, the analyses will be presented by the administration type (Study Site Personnel (HCP Administration) vs. Home Healthcare Providers/Patient/Parent/Legal Guardian/Caregiver (Caregiver Administration)) and overall.

Safety and tolerability analyses will be based on the Safety Population. All tabular summaries within this population will be presented by the icatibant exposure number. For the initial icatibant exposure, the analyses will be presented by the pubertal status (Pre-pubertal vs. Pubertal/Post-pubertal) and overall; for the subsequent icatibant exposures, the analyses will be presented by the administration type (HCP Administration vs. Caregiver Administration) and overall.

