### 7.9.10 Rescue Medication

Rescue medications will be coded using the WHO Drug Dictionary (Version 2011, Q4).

Rescue therapy is any medication used after the administration of icatibant which, in the opinion of the investigator, is immediately necessary to alleviate acute symptoms which are judged by the investigator as resultant from the current HAE attack.

Repeat administration of icatibant for the treatment of a single attack is not allowed in this study.

Antihistamines and corticosteroids are considered ineffective for the alleviation of an acute HAE attack. If administered during an acute attack that occurs during the study, they should be recorded as concomitant medications but will not be considered rescue medications.

Rescue medications administered after the treatment start and within 48+4 hours after the treatment start will be summarized by icatibant exposure number, therapeutic class, and preferred term for the Efficacy Population and the Safety Population. For medications with partial onset times, non-missing date parts will be used to determine if the rescue medication was used within 3 days of treatment. If it cannot be definitely determined that the rescue medication was used within 3 days of treatment, the rescue medication will be excluded from the summary. See Section [10.2.14](#) for the detailed definition of rescue medication.

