14.1.4.3	Rescue Medications by Icatibant Exposure Number, Therapeutic Class, and Preferred Term for Icatibant Exposure Number 2 and 3 (Efficacy Population)
14.1.4.4	Rescue Medications by Pubertal Status Stratification Group, Therapeutic Class, and Preferred Term (Safety Population)
14.1.4.5	Rescue Medications by Therapeutic Class, and Preferred Term for Icatibant Exposure Number 1 (Safety Population)
14.1.4.6	Rescue Medications by Icatibant Exposure Number, Therapeutic Class, and Preferred

Table	Table Title
	Term for Icatibant Exposure Number 2 and 3 (Safety Population)
14.1.5.1	On-Study HAE Attack and Drug Exposure for Icatibant Exposure Number 1 (Efficacy Population)
14.1.5.2	On-Study HAE Attack and Drug Exposure by Icatibant Exposure Number for Icatibant Exposure Number 2 and 3 (Efficacy Population)
14.1.5.3	Drug Exposure for Icatibant Exposure Number 1 (Safety Population)
14.1.5.4	Drug Exposure by Icatibant Exposure Number for Icatibant Exposure 2 and 3 (Safety Population)
14.1.6.1	Medical History by Pubertal Status Stratification Group, System Organ Class, and Preferred Term (Efficacy Population)
14.1.6.2	Medical History by System Organ Class, and Preferred Term for Icatibant Exposure Number 1 (Efficacy Population)
14.1.6.3	Medical History by Icatibant Exposure Number, System Organ Class, and Preferred Term for Icatibant Exposure Number 2 and 3 (Efficacy Population)
14.1.6.4	Medical History by Pubertal Status Stratification Group, System Organ Class, and Preferred Term (Safety Population)
14.1.6.5	Medical History by System Organ Class, and Preferred Term for Icatibant Exposure Number 1 (Safety Population)
14.1.6.6	Medical History by Icatibant Exposure Number, System Organ Class, and Preferred Term for Icatibant Exposure Number 2 and 3 (Safety Population)
14.2	Efficacy
14.2.1.1	Time to Onset of Symptom Relief for Composite Investigator-Assessed Symptom Scores for Icatibant Exposure Number 1 (Efficacy Population)
14.2.1.2	Time to Onset of Symptom Relief for Composite Investigator-Assessed Symptom Scores for by Icatibant Exposure Number for Icatibant Exposure Number 2 and 3 (Efficacy Population)
14.2.2.1	Time to Minimum Symptoms for Composite Investigator-Assessed Symptom Scores for Icatibant Exposure Number 1 (Efficacy Population)
14.2.2.2	Time to Minimum Symptoms for Composite Investigator-Assessed Symptom Scores by Icatibant Exposure Number for Icatibant Exposure Number 2 and 3 (Efficacy Population)

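### SAP 10.2.14 rule 2 omits limits that SAP 7.9.10 and protocol 6.7 put on rescue medication, and the SAP 7.9.10 date rule departs from protocol 10.10 undeclared, so rescue use can be miscounted

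*SAP*

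**What the plan says.** **Who counts as a rescue user.** SAP 7.9.10 and protocol 6.7 define rescue by the investigator's opinion: a drug needed at once for symptoms "judged by the investigator as resultant from the current HAE attack". Both then remove two drug classes. Of antihistamines and corticosteroids given during an attack, SAP 7.9.10 says that "they should be recorded as concomitant medications but will not be considered rescue medications". Protocol 6.7 says the same of antihistamines and glucocorticoids: "they should be recorded as concomitant medications but will not be considered as rescue medications".

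SAP 7.9.10 then sends the reader to 10.2.14 "for the detailed definition of rescue medication". That section has two alternative rules:

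- Rule 1 takes records entered as rescue on the CRF that started in the window "of a study drug exposure for an HAE attack".
- Rule 2 takes records entered as concomitant medication that started in the same window "after a study drug exposure, is not ongoing, and had an indication that include" 'HAE' or 'Swelling'.

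**Where it is reported.** Incidence of rescue use is a secondary endpoint, restricted to subjects treated during an attack (SAP 5). Rescue is tabulated for the Efficacy and the Safety Populations (SAP 7.9.10; Tables 14.1.4.1 to 14.1.4.6). The Safety Population takes every treated subject "irrespective of the presence of an HAE attack" (SAP 7.2).

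**Uncertain dates.** For its rescue summary, SAP 7.9.10 excludes a record when the available date parts do not settle whether use fell within 3 days of treatment. Protocol 10.10 gives a missing or partial rescue date the earliest possible time after treatment. SAP 8.2 states that nothing changed from the protocol's analyses.

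**The concern.** Rule 2 searches the concomitant medication records, which is where sites are told to enter antihistamines and corticosteroids. A site that follows the protocol can therefore create the very record that rule 2 reclassifies.

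The word 'Swelling' adds a second route. Skin swelling is an attack symptom, but swelling is also a listed injection site reaction (protocol 7.13.5, SAP 7.9.2). Protocol 1.2.2 reports that injection site reactions were seen in nearly all subjects in earlier studies. A text match on the indication cannot tell the two apart.

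The date rule works the other way, by removing records that the protocol would keep. The reported rescue count then depends on which passage the programmer follows. The same classification feeds the count in SAP 7.8.4 of subjects rescued before symptom relief, where five such subjects decide whether a Kaplan-Meier analysis is run. No hypothesis test is involved.

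**Working it through.** The documents state no rescue rate, so there is no figure to reproduce. The check compares the passages and then sizes one error.

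**Step 1: rule 2 as written and with the class and exposure limits added.** Take a concomitant record that already passes the window, not-ongoing and indication tests.

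| Drug class | Dose given for | Rule 2 as written | With class exclusion and rule 1's exposure condition |
|---|---|---|---|
| Antihistamine | attack | counts | does not count |
| Antihistamine | no attack | counts | does not count |
| Corticosteroid | attack | counts | does not count |
| Corticosteroid | no attack | counts | does not count |
| Other | attack | counts | counts |
| Other | no attack | counts | does not count |

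All 6 combinations count as written, and 1 counts with both limits.

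**Step 2: the symptom condition.** The one remaining row still mixes two cases: a drug given for the treated attack, and a drug given for injection site swelling after an attack dose. Only the first meets SAP 7.9.10 and protocol 6.7. Requiring that the dose was for an attack does not separate them, so the symptom condition needs its own wording.

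**Step 3: which outputs each omission can reach.**

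- Class exclusion and symptom condition: the rescue outputs of both populations.
- Exposure condition: Safety Population Tables 14.1.4.4 (pooled by pubertal status) and 14.1.4.5 ("Rescue Medications by Therapeutic Class, and Preferred Term for Icatibant Exposure Number 1 (Safety Population"). No-attack doses occur only as the initial treatment. Protocol 6.2 and 6.3 tie the two later doses to an attack, so Table 14.1.4.6, on exposures 2 and 3, is not affected by this omission.

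**Step 4: the date rules side by side.** Suppose the dose is given mid-month and the rescue record shows only that month and year.

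- Protocol 10.10: earliest possible time after treatment, so the use is kept.
- SAP 7.9.10: use within 3 days cannot be established, so the record leaves the summary.
- SAP 9.2.2, same uncertainty for an adverse event: kept as treatment-emergent. Protocol 10.10 asks for a similar approach there.
- SAP 7.9.9, same uncertainty about its 5-day window for a concomitant medication: kept.
- SAP 7.8.4: states no such exclusion and gives no rule for partial rescue dates.

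A missing time alone does not trigger the exclusion, because 10.2.14 allows 3 days in that case.

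**Step 5: size of one misclassified subject.** The denominators are the planned minimum numbers in SAP 4.1: 10 prepubertal and 10 pubertal/postpubertal subjects treated in an attack, plus 10 pubertal/postpubertal subjects treated without one. The shift is 100/n percentage points.

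- All attack-treated subjects: 100/20 = 5.0 points.
- One pubertal-status group of attack-treated subjects: 100/10 = 10.0 points.
- One no-attack subject in Table 14.1.4.5, overall: 100/30 = 3.3 points.
- The same subject in its pubertal/postpubertal column: 100/(10 + 10) = 5.0 points.

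**The case against.** The best defence on rule 2 is that SAP 7.9.10 states the class exclusion in its body text and nothing in 10.2.14 withdraws it. Read together, the limits still apply. That reading is available, and it rules out the stronger inference that the SAP reverses the exclusion or that over-counting is certain. What stands is that 7.9.10 names 10.2.14 as the detailed definition, that 10.2.14 sits among the programming conventions, and that it repeats neither limit.

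Errors from rule 2 would also be visible in part. The rescue tables are split by therapeutic class and preferred term, and there are subject listings (16.2.4.4.1 and 16.2.4.4.2). Over-counting rescue does not flatter the drug. Both remarks are fair. They reduce the harm but do not make the definition consistent.

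On dates, the exclusion is written only for the 7.9.10 summary, and few records may meet it: protocol 6.7 requires the time of rescue to be documented, and after initial treatment subjects are observed for 6 to 8 hours and contacted at 24 and 48 hours. A reader might infer that the SAP removes such records from the secondary endpoint or from the 7.8.4 analyses. The documents do not say so; 7.8.4 is silent. The conflict with protocol 10.10 and the statement in SAP 8.2 remain unanswered.

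**Conclusion.** The point holds as two inconsistencies in how rescue records are counted. Rule 2 of SAP 10.2.14, taken literally, can over-count because it lacks the class exclusion, the symptom condition and rule 1's exposure condition. The date rule in SAP 7.9.10 can under-count in that section's summary, and it is an undeclared departure from protocol 10.10.

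The documents do not give the number of affected records, and the two effects oppose each other, so the net direction is unknown. The per-subject shifts of 5.0 and 10.0 points for incidence, and of 3.3 and 5.0 points for Table 14.1.4.5, assume the planned minimum numbers and shrink if more subjects are treated. Confining the exposure condition to Tables 14.1.4.4 and 14.1.4.5 assumes that the Efficacy Population tables use attack-treated exposures only.

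A reader might infer that no-attack doses distort every Safety Population rescue table, or the secondary endpoint itself. The documents do not support either: later doses require an attack, and the endpoint is limited to subjects treated during one. The outputs are descriptive, so this should be corrected but threatens no test.

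**What to change.** In SAP 10.2.14 rule 2:

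1. Repeat the class exclusion from SAP 7.9.10 and protocol 6.7, with one term for the steroid class (the SAP says corticosteroids, the protocol glucocorticoids).
2. Require that the exposure was for an HAE attack, as rule 1 does.
3. Count a record only if its indication is the treated attack, and not injection site swelling.

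In SAP 7.9.10, and expressly for the analyses in 7.8.4, apply the date rule of protocol 10.10. If the exclusion is intended, declare and justify it in SAP 8.2.

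The cost is a few sentences of SAP wording and minor programming. No new data are needed, and nothing changes in what may be given to subjects.

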## 10.3 Appendix III: Schedule of Events

## 10.3.1 Study Schedule of Events (No Attack)

(Pubertal/postpubertal subjects only)	Screening Period	Pre-treatment (Baseline)	Treatment	Post Treatment										Follow-up		
				Day 1										Day 2	Day 3	Day 8 (±1)
Study Day		Day 1	Day 1	0	0.25	0.5	0.75	1	2	4	6	8	24	48		
Time Post Treatment (hours)					(±5) min	(±5) min	(±5) min	(±10) min	(±10) min	(±0.5) hr	(±0.5) hr	(±0.5) hr	(±4) hr	(±4) hr		
Window (hours or minutes)																
Assessments																
Informed Consent/Assent	X															
Medical History	X	X														
Documentation of HAE Attack(s) Not Treated with icatibant	X f														X	
Documentation of Pubertal Changes/Milestones																X
Confirm Documented HAE Diagnosis (via Sponsor's central lab)	X															
C1-INH Assessment	X															
Inclusion/Exclusion Assessment	X	X a														

(Pubertal/postpubertal subjects only)	Screening Period	Pre-treatment (Baseline)	Treatment	Post Treatment										Follow-up				
				Day 1										Day 2	Day 3	Day 8 (±1)	Day 90 (±7)	Month 6 (±7 days) Telephone Contact
Study Day		Day 1	Day 1	Day 1										Day 2	Day 3	Day 8 (±1)	Day 90 (±7)	
Time Post Treatment (hours)			0	0.25	0.5	0.75	1	2	4	6	8	24	48					
Window (hours or minutes)				(±5) min	(±5) min	(±5) min	(±10) min	(±10) min	(±0.5) hr	(±0.5) hr	(±0.5) hr	(±4) hr	(±4) hr					
Assessments																		
Physical Examination	X	X								X	X e			X	X			
Pubertal Status Determination b	X	X																
Menstrual Cycle History (in pubertal/postpubertal females)		X													X			
Vital Signs	X	X					X			X	X e			X	X			
ECG	X									X	X e							
Height and Weight	X	X													X			
Clinical Laboratory Tests (serum chemistry, hematology, urinalysis)		X								X				X	X			
Urine Pregnancy Test (in females of childbearing potential)	X	X													X			

(Pubertal/postpubertal subjects only)	Screening Period	Pre-treatment (Baseline)	Treatment	Post Treatment											Follow-up				
				Day 1											Day 2	Day 3	Day 8 (±1)	Day 90 (±7)	Month 6 (±7 days) Telephone Contact
Study Day		Day 1	Day 1	Day 1											Day 2	Day 3	Day 8 (±1)	Day 90 (±7)	
Time Post Treatment (hours)			0	0.25	0.5	0.75	1	2	4	6	8	24	48						
Window (hours or minutes)				(±5) min	(±5) min	(±5) min	(±10) min	(±10) min	(±0.5) hr	(±0.5) hr	(±0.5) hr	(±4) hr	(±4) hr						
Assessments																			
Reproductive Hormone Assessments (FSH, LH, estradiol, progesterone in females; FSH, LH, testosterone in males)		X								X				X	X				
Investigational Product Administration (single SC dose)			X																
Safety Follow-up Contact												X c	X c						
Injection Site Reaction Evaluation							X		X	X e	X c	X c	X						
PK Sampling d		X		X	X	X	X	X	X	X									
Immunogenicity Evaluation		X											X	X					
Concomitant Medications	X	X	X	X	X	X	X	X	X	X	X e	X c	X c	X	X				
Adverse Events			X	X	X	X	X	X	X	X	X e	X c	X c	X	X				

(Pubertal/postpubertal subjects only)	Screening Period	Pre-treatment (Baseline)	Treatment	Post Treatment										Follow-up		
				Day 1										Day 2	Day 3	Day 8 (±1)
Study Day		Day 1	Day 1													
Time Post Treatment (hours)			0	0.25	0.5	0.75	1	2	4	6	8	24	48			
Window (hours or minutes)				(±5) min	(±5) min	(±5) min	(±10) min	(±10) min	(±0.5) hr	(±0.5) hr	(±0.5) hr	(±4) hr	(±4) hr			
Assessments																

Abbreviations: FLACC = Faces, Legs, Activity, Cry, and Consolability (comportmental pain scale); FPS-R = Faces Pain Scale-Revised; FSH = follicle stimulating hormone; HAE = hereditary angioedema; hr = hour; LH = luteinizing hormone min = minute; PK = pharmacokinetic; SC = subcutaneous

- a The inclusion/exclusion criteria will be confirmed at the Pretreatment (Baseline) Visit.
- b A subject's classification as prepubertal or pubertal/postpubertal will be determined at the Day 1 pretreatment visit. Note that a subject classified as pubertal/postpubertal at screening will not require further evaluation of pubertal status during the study.
- c These assessments may be conducted by telephone contact.
- d The PK sampling times shown are for pubertal/postpubertal subjects.
- e A subject may be discharged after completion of all assessments at 6 hours post treatment, if deemed medically stable in the investigator's clinical judgment. If this is the case, the assessments scheduled for 8 hours post treatment will be omitted.
- f For all subjects who remain enrolled in the study for longer than 6 months, a telephone contact will be scheduled every 6 months to collect information concerning HAE attacks not treated with icatibant in the study.

10.3.2 Study Schedule of Events (Initial Icatibant-treated Attack)

Initial Icatibant-treated Attack (All Subjects)	Screening Period	Pre-treatment (Baseline)	Treatment	Post Treatment											Follow-up		
				Day 1									Day 2	Day 3	Day 8 (±1)	Day 90 (±7)	Month 6 (±7 days) Telephone Contact
Study Day		Day 1	Day 1	Day 1									Day 2	Day 3	Day 8 (±1)	Day 90 (±7)	
Time Post Treatment (hours)			0	0.25	0.5	0.75	1	2	4	6	8 c	24	48				
Window (hours or minutes)				(±5) min	(±5) min	(±5) min	(±10) min	(±10) min	(±0.5) hr	(±0.5) hr	(±0.5) hr	(±4) hr	(±4) hr				
Assessments																	
Informed Consent/Assent	X																
Medical History	X	X															
Documentation of HAE Attack(s) Not Treated with icatibant	X h														X		
Documentation of Pubertal Changes/Milestones																X	
Confirm Documented HAE Diagnosis (via Sponsor's Central Laboratory)	X																
C1-INH Assessment	X																
Inclusion/Exclusion Assessment	X	X a															
Physical Examination	X	X								X g	X g			X	X		

Initial Icatibant-treated Attack (All Subjects)	Screening Period	Pre-treatment (Baseline)	Treatment	Post Treatment											Follow-up	
				Day 1											Day 2	Day 3
Study Day		Day 1	Day 1	0.25	0.5	0.75	1	2	4	6	8 e	24	48			
Time Post Treatment (hours)			0	(±5) min	(±5) min	(±5) min	(±10) min	(±10) min	(±0.5) hr	(±0.5) hr	(±0.5) hr	(±4) hr	(±4) hr			
Window (hours or minutes)																
Assessments																
Pubertal Status Determination b	X	X														
Menstrual Cycle History (in pubertal/postpubertal females)		X														X
Vital Signs	X	X					X			X g	X g				X	X
ECG	X									X g	X g					
Height and Weight	X	X														X
Subject Self-assessment of HAE-related Pain Using diary FPS-R (in subjects 4 years of age and older, and before blood work, if applicable)		X					X	X	X	X f	X e,f	X	X			
Investigator Assessment of HAE Symptoms		X					X	X	X	X f	X f					

Initial Icatibant-treated Attack (All Subjects)	Screening Period	Pre-treatment (Baseline)	Treatment	Post Treatment											Follow-up				
				Day 1											Day 2	Day 3	Day 8 (±1)	Day 90 (±7)	Month 6 (±7 days) Telephone Contact
Study Day		Day 1	Day 1	Day 1											Day 2	Day 3	Day 8 (±1)	Day 90 (±7)	
Time Post Treatment (hours)			0	0.25	0.5	0.75	1	2	4	6	8 e	24	48						
Window (hours or minutes)				(±5) min	(±5) min	(±5) min	(±10) min	(±10) min	(±0.5) hr	(±0.5) hr	(±0.5) hr	(±4) hr	(±4) hr						
Assessments																			
Investigator Assessment of HAE-related Pain Using FLACC (in subjects younger than 4 years of age, and before blood work, if applicable)		X					X	X	X	X f	X f								
Clinical Laboratory Tests (serum chemistry, hematology, urinalysis)		X								X				X	X				
Urine Pregnancy Test (in females of childbearing potential)	X	X														X			
Reproductive Hormone Assessments (FSH, LH, estradiol, progesterone in females; FSH, LH, testosterone in males)		X								X				X	X				

Initial Icatibant-treated Attack (All Subjects)	Screening Period	Pre-treatment (Baseline)	Treatment	Post Treatment											Follow-up	
				Day 1											Day 2	Day 3
Study Day		Day 1	Day 1	0.25	0.5	0.75	1	2	4	6	8 e	24	48			
Time Post Treatment (hours)			0	(±5) min	(±5) min	(±5) min	(±10) min	(±10) min	(±0.5) hr	(±0.5) hr	(±0.5) hr	(±4) hr	(±4) hr			
Window (hours or minutes)																
Assessments																
Investigational Product Administration (single SC dose)			X													
Safety Follow-up Contact												X c	X c			
Injection Site Reaction Evaluation							X			X f	X f	X c	X c	X		
PK Sampling d		X		X	X	X	X	X	X	X						
Immunogenicity Evaluation		X												X	X	
Concomitant Medications	X	X	X	X	X	X	X	X	X	X f	X f	X c	X c	X	X	
Adverse Events			X	X	X	X	X	X	X	X f	X f	X c	X c	X	X	

Initial Icatibant-treated Attack (All Subjects)	Screening Period	Pre-treatment (Baseline)	Treatment	Post Treatment											Follow-up				
				Day 1											Day 2	Day 3	Day 8 (±1)	Day 90 (±7)	Month 6 (±7 days) Telephone Contact
Study Day		Day 1	Day 1	Day 1											Day 2	Day 3	Day 8 (±1)	Day 90 (±7)	
Time Post Treatment (hours)			0	0.25	0.5	0.75	1	2	4	6	8e	24	48						
Window (hours or minutes)				(±5) min	(±5) min	(±5) min	(±10) min	(±10) min	(±0.5) hr	(±0.5) hr	(±0.5) hr	(±4) hr	(±4) hr						
Assessments																			

Abbreviations: FLACC = Faces, Legs, Activity, Cry, and Consolability (comportmental pain scale); FPS-R = Faces Pain Scale-Revised; FSH = follicle stimulating hormone; HAE = hereditary angioedema; hr = hour; LH = luteinizing hormone min = minute; PK = pharmacokinetic; SC = subcutaneous

- a The inclusion/exclusion criteria will be confirmed at the Pretreatment (Baseline) Visit.
- b A subject's classification as prepubertal or pubertal/postpubertal will be determined at the Day 1 pretreatment visit. Note that a subject classified as pubertal/postpubertal at screening will not require further evaluation of pubertal status during the study.
- c These assessments may be conducted by telephone contact.
- d The PK sampling times shown are for pubertal/postpubertal subjects. Prepubertal subjects will have blood samples drawn on Day 1 prior to dosing and at 15 (±5) minutes, 30 (±5) minutes, 2 hours (±10 minutes), 4 (±0.5) hours, and 6 (±0.5) hours post dose.
- e A subject may be discharged after completion of all assessments at 6 hours post treatment, if deemed medically stable in the investigator's clinical judgment and the subject's HAE symptoms have resolved (the subject's investigator-rated symptom score = zero, denoting the absence of symptoms). If this is the case, the assessments scheduled for 8 hours post treatment will be omitted with the exception of subject self-assessment of HAE-related pain using the diary FPS-R.
- f If the subject's HAE symptoms have not resolved at 6 hours post treatment (the subject's investigator-rated symptom score ≠ zero) and the subject is not to be discharged after completion of assessments at the 6-hour time point, the assessments indicated will be performed at both 6 AND 8 hours post treatment.
- g If the subject's HAE symptoms have not resolved at 6 hours post treatment (the subject's investigator-rated symptom score ≠ zero) and the subject is not to be discharged after completion of assessments at the 6-hour time point, the assessments indicated will be performed at either 6 OR 8 hours post treatment.
- h For all subjects who remain enrolled in the study for longer than 6 months, a telephone contact will be scheduled every 6 months to collect information concerning HAE attacks not treated with icatibant in the study.

